Telephone call	X					X††††			X\$\$\$\$\$
Passive surveillance	X		Participants will be instructed to contact the site if they experience symptoms of a COVID-19-like illness at any time during the study.						

Visit (V) / Contact	Collection of information in the CRF	V01	V02	V03	V04	Telephone Call	V05	V06	V07 or Safety Follow-up Call§§§§
Study timelines (Day [D])		D01	D09	D22	D36	D43	D113	D181	D366
Time Interval (days)			V01 + 8 days	V01 + 21 days	V01 + 35 days	V01 + 42 days	V01 + 112 days	V01 + 180 days	V01 + 365 days
Time windows (days)		N/A	[+2 days]	[+7 days]	[+7 days]	[+2 days]	[+7 days]	[+14 days]	[+14 days]
Visit procedures:									
Active surveillance calls	X					TC to occur every 2 weeks after the D43 contact until D181§§§ (See also Schedule of Activities Table 1.3 for follow-up)			
Collection of SAEs, AESIs ****, and MAAEs	X					To be reported at any time during the study			
Collection of pregnancies	X								
End of phase participation record††††	X					X	X	X	
End of active phase participation record	X								X
12 Month Follow-up participation record (only for those discontinued early) §§§§	X								X

Abbreviations: Ab, Antibody; AE, adverse event; AESI, adverse event of special interest; BL, blood sample (#); CRF, Case Report Form; DC, Diary Card; IRT, interactive response technology; MAAE, medically attended adverse event; S, Spike; SAE, serious adverse event; SARS-CoV-2, severe acute respiratory syndrome coronavirus 2; V, visit; VAC, vaccination

*Targeted physical examination based on the participant's medical history and the examiner's medical judgment will be performed at V01.

† Urine pregnancy test is applicable to childbearing potential female participant (to be considered of non-childbearing potential, a female must be post-menopausal for at least 1 year or surgically sterile). Urine pregnancy test is to be performed before vaccination.

‡ Safety laboratory assessments will include: Serum Chemistries (liver enzymes / Chem 7, lipase, and amylase); hematology (complete blood count with differential); Urinalysis; Microscopy. In cases of abnormal safety laboratory results, unscheduled visits may occur, based on Investigator's judgment.

§ BL0001 and the first safety laboratory assessment sample will be collected at pre-vaccination (baseline).

Visit (V) / Contact	Collection of information in the CRF	V01	V02	V03	V04	Telephone Call	V05	V06	V07 or Safety Follow-up Call§§§§
Study timelines (Day [D])		D01	D09	D22	D36	D43	D113	D181	D366

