Time Interval (days)			V01 + 8 days	V01 + 21 days	V01 + 35 days	V01 + 42 days	V01 +112 days	V01 + 180 days	V01 + 365 days
Time windows (days)		N/A	[+2 days]	[+7 days]	[+7 days]	[+2 days]	[+7 days]	[+14 days]	[+14 days]
Visit procedures:									

** Participants will use this DC1 to record information about solicited reactions, unsolicited AEs, SAEs, and AESIs from D01 to D08 after vaccination and will continue to record information about unsolicited AEs, SAEs, and AESIs from D09 to V03.

†† The Investigator or an authorized designee will remind the participants to bring back the DC at the next visit and will answer any questions.

‡‡ The Investigator or an authorized designee will interview the participants to collect the information recorded in the DC and will attempt to clarify anything that is incomplete or unclear.

§§ Participants will use this DC2 for SAEs, AESIs, and COVID-19-like illness follow-up from V03 to V04.

*** Participants will use this DC3 for SAEs, AESIs, and COVID-19-like illness follow-up from V04 to V05.

††† Participants will use this DC4 for SAEs, AESIs, and COVID-19-like illness follow-up from V05 to V06.

†††† Participants will use this DC5 for SAEs, AESIs, and COVID-19-like illness follow-up from V06 to V07.

§§§ Prior to these specified time-points, active surveillance will still occur during the established contacts (phone calls and visits).

**** AESIs (serious and non-serious) will be collected throughout the study as SAEs to ensure that events are communicated to the Sponsor in an expedited manner and followed-up until the end of the follow-up period or resolution, as per the assigned causal relationship. These include: Anaphylactic reactions, Generalized convulsion, Thrombocytopenia, Lacrimal and salivary disorders (tearing, dry mouth, dry eyes), any new-onset chronic medical conditions, and potential immune-mediated diseases.

†††† In case of participant discontinuation at a visit, the entire visit will be completed

††††† During the D43 telephone call, staff will review the DC3 pertaining to SAE, AESI, and COVID-19-like illness between V04 and the call and will remind the participant to bring back the DC3 for V05. This telephone call will NOT be collected in the CRF.

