** Participants will use this DC1 to record information about solicited reactions, unsolicited AEs, SAEs, and AESIs from D01 to D08 after vaccination and will continue to record information about unsolicited AEs, SAEs, and AESIs from D09 to V02.

†† The Investigator or an authorized designee will remind the participants to bring back the DC at the next visit and will answer any questions.

‡‡ The Investigator or an authorized designee will interview the participants to collect the information recorded in the DC and will attempt to clarify anything that is incomplete or unclear.

§§ Participants will use this DC2 to record solicited reactions, unsolicited AEs, SAEs, and AESIs (from V02 to V03) and will continue to collect unsolicited AEs, SAEs, and AESIs (from V03 to V04).

*** Participants will use this DC3 for unsolicited AEs follow-up until D43 and SAEs, AESIs, and COVID-19-like illness follow-up from V04 to V05.

††† Participants will use this DC4 for SAEs, AESIs, and COVID-19-like illness follow-up from V05 to V06.

‡‡‡ Participants will use this DC5 for SAEs, AESIs, and COVID-19-like illness follow-up from V06 to V07.

§§§ During the D09 telephone call, staff will review the DC1 for solicited reactions from D01 to D08 after vaccination, inquire whether the participant experiences any SAE or AESI not yet reported, and remind the participant to bring back DC1 for V02. This telephone call will NOT be documented in the CRF.

**** Prior to these specified time-points, active surveillance will still occur during the established contacts (phone calls and visits).

†††† AESIs (serious and non-serious) will be collected throughout the study as SAEs to ensure that events are communicated to the Sponsor in an expedited manner and followed-up until the end of the follow-up period or resolution, as per the assigned causal relationship. These include: Anaphylactic reactions, Generalized convulsion, Thrombocytopenia, Lacrimal and salivary disorders (tearing, dry mouth, dry eyes), any new-onset chronic medical conditions, and potential immune-mediated diseases.

†††† In case of participant discontinuation at a visit, the entire visit will be completed.

§§§§ During the D43 telephone call, staff will review the DC3 pertaining to unsolicited AEs, SAE, AESI, and COVID-19-like illness between V04 and the call and will remind the participant to bring back the DC3 for V05. This telephone call will NOT be documented in the CRF.

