2.3.3 Overall Benefit-Risk Conclusion

Considering the significant medical need, scale of the pandemic, urgent requirement for measures to address the pandemic, together with actions taken to minimize risk to participants enrolled in the study, there is no unreasonable and significant risk of illness or injury for the participants.

3 Objectives and Endpoints

The study objectives and the corresponding endpoints are described in [Table 3.1](#).

Table 3.1: Objectives and endpoints

Objectives	Endpoints
Primary	
Immunogenicity To describe the neutralizing antibody profile at D01, D22, and D36 of each study intervention group.	Immunogenicity Neutralizing antibody titers will be measured with the neutralization assay. 
• Antibody titer at D01, D22, and D36• Fold-rise (fold-rise in serum antibody neutralization titer post-vaccination relative to D01) at D22, and D36• 2-fold and 4-fold rise in serum neutralization titer (post/pre) relative to D01 at D22, and D36• Occurrence of neutralizing antibody seroconversion, defined as baseline values below lower limit of quantification (LLOQ) with detectable neutralization titer above assay LLOQ at D22 and D36
Safety To describe the safety profile of all participants in each age group and each study intervention group up to 12 months post-last dose.	Safety 
• Presence of unsolicited systemic AEs reported in the 30 minutes after each injection• Presence of solicited (pre-listed in the participant's diary card and Case Report Form [CRF]) injection site reactions and systemic reactions occurring up to 7 days after each injection• Presence of unsolicited AEs reported up to 21 days after each injection• Presence of medically attended adverse events (MAAEs) throughout the study• Presence of serious adverse events (SAEs) and adverse events of special interest (AESIs) throughout the study• Presence of out-of-range biological test results up to 7 days post-last dose (ie, up to D09 for Cohort 1 and up to D30 for Cohort 2)

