8.4.1 Time Period and Frequency for Collecting AE and SAE Information

Immediate Post-vaccination Observation Period

Participants will be kept under observation for 30 minutes after each vaccination to ensure their safety. The post-vaccination observation should be documented in the source document.

Reactogenicity

Solicited injection site reactions will be collected from D01 to D08 after each vaccination.

Solicited systemic reactions will be collected from D01 to D08 after each vaccination.

The solicited injection site reactions and systemic reactions that are pre-listed in the diary cards and CRF, together with the intensity scales, are presented in [Appendix 10.3.5.1.1](#).

Unsolicited Adverse Events

Unsolicited AEs include unsolicited non-serious AEs and SAEs. The intensity grading scale for unsolicited non-serious AEs is presented in [Appendix 10.3.5.1.2](#).

Unsolicited non-serious AEs will be collected from D01 to D22 after each vaccination.

SAEs will be collected and assessed throughout the study, from inclusion until 12 months after the last vaccination (up to D366 for Cohort 1 and up to D387 for Cohort 2). However, before the first study intervention administration, only SAEs related to study procedures are to be collected (eg, SAEs related to blood sampling).

Medical occurrences that begin before the start of study intervention but after obtaining informed consent will not be recorded on the AE section of the CRF.

All SAEs will be recorded and reported to the Sponsor or designee immediately and under no circumstance should this exceed 24 hours, as indicated in [Appendix 10.3](#). The Investigator will submit any updated SAE data to the Sponsor within 24 hours of it being available.

Investigators are not obligated to actively seek AE or SAE after conclusion of the study participation. However, if the Investigator learns of any SAE, including a death, at any time after a participant has been discharged from the study, and he/she considers the event to be reasonably related to the study intervention or study participation, the Investigator must promptly notify the Sponsor.

Medically Attended Adverse Events (MAAEs)

MAAEs will be collected at any time during the study.

Adverse Events of Special Interest (AESIs)

AESIs will be collected at any time during the study.

See [Section 8.4.6](#) for the list of AESIs.

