8.4.2 Method of Detecting AEs and SAEs

Individual diary cards, specifically designed for this study by the Sponsor and provided to the study sites, will be given to study participants for the recording of daily safety information. These diary cards will include pre-listed terms and intensity scales as well as areas for free text to capture additional safety information or other relevant details. Participants will also be provided with rulers for measuring the size of injection site reactions, and with standard digital thermometers for measuring daily temperatures. To ensure consistency of reporting, the study sites will instruct participants on how to correctly use these tools.

At specified intervals, the Investigator or an authorized designee will interview the participants to collect the information recorded in the diary card and will attempt to clarify anything that is incomplete or unclear. All clinical study information gathered by the study site will be reported electronically by the Investigator or authorized designee using a web-based CRF. Any information that was not documented in the diary card will first be captured in the source document and then reported electronically.

The 12-month (post-last injection) follow-up will be done by interviewing participants either during a visit or over the telephone using a questionnaire to capture SAEs and AESIs, if applicable.

The method of recording, evaluating, and assessing causal relationship of AE and SAE and the procedures for completing and transmitting SAE reports are provided in [Appendix 10.3](#).

Care will be taken not to introduce bias when detecting AEs and/or SAEs. Open-ended and non-leading verbal questioning of the participant is the preferred method to inquire about AE occurrences.

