8.4.7 Medically Attended Adverse Events

MAAEs will be collected using the same process as other AEs. See [Appendix 10.3.1](#) for definition of MAAEs.

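### MAAEs are a primary safety endpoint for the whole study, but after the unsolicited AE window no described instrument prompts for those that are non-serious, not AESIs and not COVID-19-like illness

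*Protocol*

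**What the plan says.** **The commitment.** Protocol Table 3.1 lists among the primary safety endpoints: "Presence of medically attended adverse events (MAAEs) throughout the study". Section 8.4.1 says "MAAEs will be collected at any time during the study", and the row of the Schedule of Activities that covers SAEs, AESIs and MAAEs says "To be reported at any time during the study". SAP Section 4.4.1.4.8 analyses MAAEs for the period up to 21 days after the last injection, for the 6- and 12-month follow-up periods, and for the whole study.

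**The means of collection.** The footnotes to Protocol Tables 1.1 and 1.2 state what each diary card (DC) is for. For Cohort 1 they say "Participants will use this DC3 for SAEs, AESIs, and COVID-19-like illness follow-up from V04 to V05". In both cohorts the next card reads "Participants will use this DC4 for SAEs, AESIs, and COVID-19-like illness follow-up from V05 to V06". Section 8.4.2 describes the 12-month follow-up as an interview "using a questionnaire to capture SAEs and AESIs, if applicable". On process, Section 8.4.7 says only "MAAEs will be collected using the same process as other AEs", while Section 8.4.1 limits that process: "Unsolicited non-serious AEs will be collected from D01 to D22 after each vaccination".

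**The concern.** The endpoint runs for about a year after the last injection, but the tools described for most of that year are built for other event types. The MAAE definition in Protocol Section 10.3.1 sets a low threshold: contacting a physician by telephone or e-mail counts. Participants easily forget such contacts, or do not think them worth mentioning, unless someone asks.

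A late event that is mentioned but not recognised as medically attended also drops out of the tables. Under SAP Section 4.4.1.2.4, an unsolicited AE with onset more than 22 days after injection is tabulated only if it is an SAE, MAAE, AESI or new-onset chronic condition (NOCMC); otherwise it is only listed.

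At stake is whether the 6- and 12-month MAAE tables, which report a primary endpoint, can be read as estimates of how often these events occurred.

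**Working it through.** **Step 1. Compare each late instrument with the endpoint.** The contents below come from the footnotes to Protocol Tables 1.1 and 1.2 and from Sections 8.2.2.2 and 8.4.2.

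| Instrument after the unsolicited AE window | Described content | MAAEs named? |
|---|---|---|
| Cohort 1 DC2 to DC5 | SAEs, AESIs, COVID-19-like illness | No |
| Cohort 1 D43 call | SAEs, AESIs, COVID-19-like illness | No |
| Cohort 2 DC3 after D43, DC4, DC5 | SAEs, AESIs, COVID-19-like illness | No |
| Memory Aid and call for early discontinuers, both cohorts | SAEs, AESIs | No |
| 12-month questionnaire | SAEs, AESIs | No |
| Two-weekly surveillance calls to D181 or D202 | COVID-19 illness | No |

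Cohort 2 DC2 and the Cohort 2 D43 call are not in the table. They cover unsolicited AEs and so already reach MAAEs within the window.

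**Step 2. See whether Section 8.4.7 closes the gap.** It sends MAAEs through the same process as other AEs. For non-serious unsolicited AEs, Section 8.4.1 ends that process at D22 after each vaccination: study day D22 in Cohort 1, and D43 in Cohort 2, whose second injection is on D22. After that, the reference leads to no active process for a non-serious event.

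**Step 3. Narrow the class of events.** Three kinds of late MAAE have their own prompt: SAEs; AESIs, which include new-onset chronic conditions and potential immune-mediated diseases (Section 8.4.6); and COVID-19-like illness, for which sites record office, urgent-care and emergency visits (Section 8.2.2.2). What remains is MAAEs that are non-serious, not AESIs and not COVID-19-like illness.

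**Step 4. Length of the unprompted period.** Share = (last study day − last day of window) / last study day, on nominal days.

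- Cohort 1: (366 − 22) / 366 = 344 / 366 = 94.0%.
- Cohort 2: (387 − 43) / 387 = 344 / 387 = 88.9%.
- Both, weighted by planned size. Cohort 1 has 5 × 20 + 5 × 10 = 150 participants. Cohort 2 has 4 × 20 + 2 × 60 + 3 × 10 + 2 × 30 = 290. The total of 440 matches the plan. The share is (440 × 344) / (150 × 366 + 290 × 387) = 151,360 / 167,130 = 90.6%.
- Surveillance calls stop at V06. From there to V07 is 366 − 181 = 185 days in Cohort 1 and 387 − 202 = 185 days in Cohort 2, bridged only by DC5.

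**Step 5. What can be said about missed events.** The plan gives no MAAE rate and no capture probability, so the shortfall cannot be computed. As an illustration resting on assumptions only, take an arm of n = 30, a true risk p of a late MAAE of this kind, and a captured share s. The expected number of participants recorded is n × p × s.

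| s | p = 10% | p = 30% |
|---|---|---|
| 100% | 3 | 9 |
| 75% | 2.25 | 6.75 |
| 50% | 1.5 | 4.5 |
| 25% | 0.75 | 2.25 |

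If s is the same in vaccine and placebo, the recorded risk difference is s × (p1 − p0), while the ratio p1 / p0 is unchanged. With assumed risks of 20% and 10% and s = 50%, the recorded risks are 10% and 5%: a difference of 5 points instead of 10, with the ratio still 2.

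**The case against.** **The protocol does require collection.** MAAEs share a row in the Schedule of Activities. Section 8.4.2 provides free-text space on the cards, interviews at specified intervals and open-ended questioning as the preferred method. The MAAE definition includes advice sought at a study visit, and the SAP expects MAAEs with late onset. This stands: some late MAAEs will be captured. A reader might infer that they are not collected at all after the window, or that medical contacts are never asked about. The documents do not support that. Nor are COVID-19-like illnesses a small exception: under Section 8.2.2.1, cough or fever alone can qualify.

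**The forms are not in the documents.** The footnotes may be incomplete summaries. The DC1 notes omit COVID-19-like illness, although surveillance for it starts at vaccination. This also stands, and it is why the conclusion is that under-collection is likely, not certain. Against it, the Cohort 2 DC3 note separates what is asked up to D43 from what is asked afterwards, so content was specified with some care, and the SAP repeats the notes. If the real forms do ask about MAAEs, the protocol's description still needs correcting.

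**The percentages measure time, not harm.** Correct. Neither figure says that 94% or 89% of late MAAEs are missed. SAP Section 4.4.1.4.8 also excludes from the analysis MAAEs with onset on or after receipt of a non-study COVID-19 vaccine, so the analysed late period is shorter for participants who receive one.

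**Placebo participants use the same instruments.** Within each cohort this is so, under observer-blinding, and the results are descriptive. A reader might infer that the gap makes the vaccine look safer than placebo. Roughly equal under-capture would not do that by itself.

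**Conclusion.** The concern holds for a limited class of events. MAAEs that are non-serious, not AESIs and not COVID-19-like illness are likely to be under-collected from D23 to D366 in Cohort 1 and from D44 to D387 in Cohort 2, 344 days in each. The main consequence is that absolute late MAAE rates are biased low in every arm and absolute differences from placebo are reduced. A reassuringly low 6- or 12-month rate could partly reflect what the forms ask.

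The conclusion rests on two assumptions: that the forms match their description in the protocol, and that prompted recall of medical contacts is more complete than spontaneous report. The inconsistency between the endpoint and the described instruments needs neither assumption. The number of missed events cannot be derived from the documents.

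**What to change.** Add MAAEs, with one question on unplanned medical contact since the last visit, to:

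- Cohort 1 DC2 to DC5 and the Cohort 1 D43 call;
- Cohort 2 DC3 (for the time after D43), DC4 and DC5;
- the Memory Aid and the early-discontinuation safety call;
- the 12-month questionnaire.

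Cohort 2 DC2 and the Cohort 2 D43 call need no change. Section 8.4.7 should state which process applies to MAAEs once the unsolicited AE window has closed.

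For follow-up already completed, new prompts come too late; Protocol Section 9.5 records a partial database lock by Amendment 1. The SAP and the clinical study report should then state that late MAAEs were not systematically prompted, and qualify the 6- and 12-month tables accordingly.

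The cost is a slightly longer interview and an amendment to the forms with ethics approval; no new visit is needed. A change made mid-study would also mix two capture methods over calendar time, so the date of the switch should be recorded and reported.

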2.1 Study Rationale

The current first-in-human study will evaluate the immunogenicity and safety of the candidate vaccine with the goal of selecting a formulation, or formulations, and a dosing schedule to proceed to efficacy evaluation as rapidly as possible.

2.2 Background

SARS-CoV-2 is a novel coronavirus that emerged in the human population and has led to a pandemic of acute respiratory disease named COVID-19. Coronaviruses are a family of large, enveloped, positive-sense, single-stranded ribonucleic acid (RNA) viruses that infect a wide variety of mammalian and avian species. The viral genome is packed into a capsid comprised of the viral nucleocapsid protein, which is in turn surrounded by an envelope. Viral proteins associated with the envelope include the S protein, which mediates viral attachment and entry into cells.

The burden of SARS-CoV-2 morbidity and mortality has been catastrophic with greater than 815,000 deaths recorded since first emerging in December 2019 among over 23.7 million confirmed cases (as of 25 August 2020) (2). In many locations, the rapid emergence of COVID-19 has overwhelmed the capacity of health systems to provide care for COVID-19-affected patients, let alone unaffected patients. Interventions to reduce transmission through reduction of population contact has had economic consequences. A safe and effective vaccine would be a vital tool to address the significant medical and societal burden caused by the pandemic.

The CoV2 preS dTM recombinant protein vaccine belongs to the pharmacotherapeutic group of “Other viral vaccines”. The vaccine contains recombinant S protein, stabilized to maintain native prefusion trimer configuration as present on the viral envelope.

Further details of the chemistry, pharmacology, and safety of the CoV2 preS dTM recombinant protein vaccine are provided in the Investigator’s Brochure (IB).

